7.5.1.2 Effect of intervention on PrEP continuation at 60 days

Analysis Population: Cluster-Randomized Control Trial Population

The primary analysis will aim to estimate the effectiveness of the pharmacy-delivered PrEP intervention as measured by the number of PrEP continuations by 60 days at each pharmacy

among the clients enrolled in the cluster-randomized control trial phase of the study who initiated PrEP.

Descriptive statistics

A table will be produced giving descriptive statistics of PrEP continuation by study arm. A figure similar to that described in 7.5.1.1 will be generated.

Inference

The primary analysis (including sensitivity analyses) will utilize the same approach as described for PrEP initiation (7.5.1.1).

7.5.1.3 Secondary Analyses

For the outcome of PrEP continuation at 60 days, we will conduct a **secondary analysis** of the proportion of participants continuing PrEP at 60 days among those who initiated PrEP. In particular, we will estimate the risk difference of PrEP continuation between each intervention arm and the SOC arm using a Poisson generalized estimating equations (GEE) model with identity link and robust standard errors (Pedoza and Truong, BMC Med Res Methodology, 2016). The outcome will be self-reported PrEP continuation from the brief client survey. The model will include study arm as a four-level categorical (nominal) variable and adjust for county to account for the stratified randomization procedure. To account for varying cluster size (number of PrEP initiators), we will use an independent working correlation matrix and weights for cluster size (Wang et al., Contemp Clin Trials, 2022). Missingness will be addressed as described in Section 6.7. In the event that this model does not converge or yields invalid estimates (e.g., risk differences or confidence intervals outside of ± 1), we will instead fit a modified Poisson GEE model—i.e., a GEE with log link and robust standard errors (Yelland et al., AJE, 2011)—to estimate the relative risk comparing each intervention arm to the SOC arm. Importantly, as this analysis is restricted to those who have initiated PrEP, randomization is not maintained. Thus, we would need to adjust for factors related to initiation in order to remove the bias incurred by selecting only those who initiate (Hernan and Hernandez-Diaz, Clin Trials, 2012).

Additionally, **secondary analyses** for PrEP initiation and continuation at 60 days will be conducted to evaluate whether the effect of the intervention differs by urban/rural pharmacy status, location in Western vs. Eastern Kenya, or by the proportion of enrolled individuals who (1) are female or (2) over the age of 25. This will be done by adding two terms to the model described in Section 7.5.1.1: the main effect of the subgroup variable (e.g., percent female) and an interaction between the categorical intervention variable and the subgroup variable. As part of this analysis, we will estimate the intervention effects within each subgroup.

In addition, **secondary analyses** for both PrEP initiation and PrEP continuation with 60 days among the clients in the three intervention arms will be performed to compare each of the three intervention arms to each other. The approaches will be identical to that described in Sections 7.5.1.1, with the caveat that the outcome (PrEP initiation or PrEP continuation) will be computed from the pharmacy records, which is available for all three intervention arms and will be a more complete data source than the 60-day follow-up survey. Because the pharmacy data precisely reflects the day initiation or refill takes place, the computation will use a cutoff of exactly 60 days from initial pharmacy-based screening.

A **secondary descriptive analysis** will be performed to compare the data on PrEP initiation by 60 days and PrEP continuation by 60 days from the brief clients surveys versus clinic records

among those in the SOC arm (Arm 4). In particular, we will compare the number (1) initiating PrEP within 60 days and (2) continuing PrEP by 60 days between these two data sources. A similar analysis will be performed for the three intervention arms to compare the number of PrEP initiations and continuations based on the brief client surveys versus the pharmacy records.

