4.5 Sample size and power

We had planned to analyze the PrEP and PEP initiation and continuation outcomes as binary outcomes, using an individual-level analysis. However, in September 2023, it became apparent that the denominators that would be used in these estimates (number enrolled) would vary greatly across arms (and indeed would be affected by which arm a pharmacy was randomized to) and would likely lead to biased estimates of the proportions initiating/continuing in each arm. In particular, the intervention is thought to (a) have an effect on likelihood of enrollment and (b) have an effect on likelihood of PrEP/PEP initiation (and thus continuation); we would like to capture the total effect of the intervention, i.e., both (a) and (b). However, by only considering individuals who were enrolled (which corresponds to the previous analytic approach), we would only capture (b), and would be ignoring (a).

Thus, we are instead pursuing a cluster-level analysis of the initiation and continuation outcomes, where each cluster (pharmacy) is summarized by the number of initiations/continuations over the course of the study, accounting for pharmacy size (i.e., pharmacy flow). This is reflected in the analytic approach described below.

The anticipated number of PrEP and PEP initiations and continuations within 60 days of pharmacy screening per pharmacy in each study arm over 16 months of implementation are given in **Table 2**. Estimates of the total counts per pharmacy in each arm were based on those observed in pilot studies of pharmacy-delivered PrEP and PEP services: (1) one which offered PrEP for a fee of 350 KES in 4 pharmacies—informing Arm 1 PrEP initiation and continuation estimates (Ortblad et al., J Int AIDS Soc. 2023), and (2) another which offered PrEP and PEP services for free in 12 pharmacies—informing Arm 2 PrEP initiation and continuations estimates, as well as PEP initiation and continuation estimates (Roche et al., CROI 2023). The estimates in other arms were based on the hypothesized difference between the arms—with the hypothesis that Arm 3 (implementor-sustained with HTS counselor support) would perform best, followed by Arm 2 (implementor-sustained), Arm 1 (clients-sustained), and Arm 4 (SOC referral). The PrEP continuation estimates in Arm 4 (SOC referral) were additionally informed by the Partners Scale-up Project, with delivered PrEP services in 24 public clinics in Kenya. Based

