We will estimate the ratio of PrEP initiation rates (number of initiations per clients served at the pharmacy, accounting for pharmacy volume over the implementation period) comparing each intervention arm to the SOC arm using a Poisson generalized linear model with log link and robust standard errors. The model will allow for overdispersion to account for increased variability in rates. The outcome will be number of self-reported PrEP initiations from the 60-day brief client survey in each pharmacy. A cluster-level analysis was chosen for the outcome of PrEP initiation because the number of individuals enrolling in the study at a given pharmacy was found to be heavily dependent upon the study arm of the pharmacy. Thus, the available denominator for the individual-level PrEP initiation outcome, number of individuals enrolled in the study, was a poor proxy for the quantity of interest, number of pharmacy PrEP candidates (i.e., individuals determined at risk of HIV acquisition who meet the pharmacy PrEP prescribing checklist criteria). Instead, we will pursue a cluster-level analysis where the outcome is number of initiations at each pharmacy and we account for pharmacy volume as a way to make fair comparisons across pharmacies.

The model will include study arm as a four-level categorical (nominal) variable and a continuous offset variable reflecting pharmacy volume (number of clients per unit time). Pharmacy volume will be measured as the number of transactions per month. Estimates of monthly volume will be obtained up to three times in each pharmacy during the course of the study (to account for seasonal variations); missing observations will be imputed, and we will take the average of the three assessments. To account for the stratified randomization procedure, we will adjust for county as a categorical (nominal) variable. As noted in Section 6.7, our missing imputation strategy (i.e., imputing missing outcome data as failures) will not affect the primary analysis of the pharmacy-level count data and will only influence the secondary analysis described in Section 7.5.1.3.

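### Effect modification by sex and age is tested through each pharmacy's share of enrolled clients, an ecological and very imprecise measure taken after randomisation; counts by sex and age group should be added

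*SAP*

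**What the plan says.** SAP section 7.5.1.3 plans effect-modification analyses of 60-day PrEP initiation and continuation by urban or rural status, by Western or Eastern Kenya, "or by the proportion of enrolled individuals who (1) are female or (2) over the age of 25". The model of section 7.5.1.1, with one count per pharmacy, is extended by "the main effect of the subgroup variable (e.g., percent female) and an interaction between the categorical intervention variable and the subgroup variable". The section then states that "we will estimate the intervention effects within each subgroup".

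On enrolment, section 4.5 says that the intervention is thought to "have an effect on likelihood of enrollment". Section 7.5.1.1 reports that the "number of individuals enrolling in the study at a given pharmacy was found to be heavily dependent upon the study arm of the pharmacy". On these grounds the SAP gave up enrolled clients as a denominator and moved to pharmacy counts offset by pharmacy volume.

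Section 6.2 lists age and sex in the Arm 1 to 3 pharmacy records and brief demographics in the client survey for all arms. Section 7.4 tabulates enrolment characteristics by arm.

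**The concern.** Three things sit badly together.

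- The modifier describes the make-up of the enrolled group, which forms after randomisation by a process that the SAP itself says the arm affects. If the arms also draw in a different mix of clients, adjusting for the share and letting it interact with arm can distort both the interaction and the arm effects read from the model.
- The question is ecological. The model asks whether pharmacies with more women among their enrolled clients show a larger effect. It does not ask whether women do.
- A continuous share defines no subgroups. An effect in women or in men can be read from this model only at 100% or 0% female, which is likely to lie far outside the data.

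At stake is the reading of the sex and age results. A wide interval around no interaction could be reported as no difference by sex or age when the analysis could hardly have found one.

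**Working it through.** **Inputs from the SAP.** 15 pharmacies per arm (section 4.2); CV 0.25 and Bonferroni alpha 0.05/3 (section 4.5); PrEP initiations per pharmacy 16.13 in Arm 1 and 10.08 in Arm 4 (Table 3); allocation by county (Table 1); enrolment target 5,865 (section 4.5).

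**Assumptions not in the SAP.** Between-pharmacy SD of the female share 0.05 to 0.20; sex split 30:70 to 70:30; equal pharmacy volume; and, for the bias check, a sex difference in baseline rates and an arm effect on enrolment mix.

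**Step 1: reproduce the SAP's power.** Power = Φ(√[(c−1)(λ1−λ0)² / ((λ1+λ0) + CV²(λ1²+λ0²))] − z), with c = 15 and z = 2.394. For Arm 1 versus Arm 4 PrEP initiation, the root is 3.240 and power is 80.1% (Table 4: 80%). PrEP continuation gives 23.2% (23%) and combined continuation 48.4% (48%). The inputs are therefore the SAP's own. It states no precision for the effect-modification analyses.

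**Step 2: planned model, by formula.** SE of the log ratio of rate ratios (0% to 100% female) = √[(1/λ1 + 1/λ0 + 2CV²) / (14·SD²)]. The numerator is 0.0620 + 0.0992 + 0.1250 = 0.2862.

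| SD of share | SE | 95% CI factor (×/÷) | Ratio detectable, 80% power, two-sided 0.05 |
|---|---|---|---|
| 0.05 | 2.86 | 272 | about 3,000 |
| 0.10 | 1.43 | 16.5 | 55 |
| 0.15 | 0.95 | 6.5 | 14 |
| 0.20 | 0.72 | 4.1 | 7.4 |

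**Step 3: sex-specific counts, by formula.** SE = √[Σ(1/events per sex and arm)/15]; pharmacy variation common to both sexes cancels. At 50:50, 2/8.065 + 2/5.04 = 0.645, and √(0.645/15) = 0.21. Adding a sex-specific CV of 0.25 gives √((0.645 + 4×0.0625)/15) = 0.24. Over splits of 30:70 to 70:30 the SE is 0.21 to 0.26, the CI factor 1.5 to 1.7 and the detectable ratio 1.8 to 2.1.

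**Step 4: simulation of both models.** The formulas ignore sampling noise in the observed share and, for the counts, variation in sex mix between pharmacies. With both included (60 pharmacies, 600 runs per setting, 50:50 split, equal baseline rates, true log ratio 0.41):

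| SD of share | SD of estimate, planned | SD of estimate, counts | Ratio |
|---|---|---|---|
| 0.05 | 1.94 | 0.22 | 8.8 |
| 0.10 | 1.33 | 0.26 | 5.1 |
| 0.15 | 0.94 | 0.32 | 2.9 |
| 0.20 | 0.79 | 0.37 | 2.1 |

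Across repeated simulations of this kind the ranges were about 0.7 to 2.1 and 0.2 to 0.4. With a true ratio of 2.0, the planned model rejected in 10% to 17% of runs, and the counts in 76% falling to 40%, as the SD rose from 0.05 to 0.20.

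**Step 5: direction of bias.** With 5,865 enrolled in proportion to Table 3, an Arm 4 pharmacy enrols 5,865 × 26.08/3,519 = 43.5 clients. Reliability of its observed share, SD²/(SD² + 0.25/43.5), is 0.30, 0.64, 0.80 and 0.87 at the four SDs.

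- Equal baseline rates, true log ratio 0.69: the planned mean was 0.36 at SD 0.05 but 0.59 to 0.69 at SD 0.10 to 0.20.
- Women initiating at three times the male rate, and intervention arms shifting enrolment towards women by 0.5 on the log-odds scale (SD 0.10 and 0.20): a true null gave +0.44 and +0.30, and a true 0.69 gave 1.43 and 1.89. Under the null, the Arm 1 rate ratio at the mean share fell from a true 1.60 to 1.51 and 1.46.
- Sex-specific counts in the same four settings averaged −0.03 to 0.00 under the null and 0.69 to 0.71 for 0.69.

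**Step 6: are the data there?** The share can be computed only from each enrolled client's sex and age. The same data allow initiations and continuations to be counted by sex and age group.

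**The case against.** The strongest reply is that all the listed modifiers are analysed at pharmacy level, in keeping with a deliberate cluster-level design. Whether the effect varies with a pharmacy's client mix is a fair question, section 7.5.1.3 never says outright that it will estimate an effect in women, and the phrase about subgroups suits urban/rural status and region well. This is a secondary analysis with no power claim, and the primary estimates are untouched. All of that stands, and it is why the planned analysis should stay. It does not supply an answer about sex or age.

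The alternative also has limits. The team was unblinded on 6 November 2025 (section 7.7), volume is not split by sex or age, and Arm 4 counts are small (10.08 initiations and 6.05 continuations per pharmacy, about halved by splitting). These limits are real, but the precision in the working already allows for the small initiation counts.

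A reader might infer four stronger things that the SAP does not support.

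- *That the SAP says the share depends on arm.* It says so only of the likelihood and number of enrolments.
- *That the bias is towards no difference.* Clear attenuation appeared only at a share SD of 0.05; elsewhere the bias was small or upward.
- *That the share is almost a function of the outcome because most enrolled clients initiate.* The outcome here is PrEP: 1,119 of 5,865 is 19%, and section 7.7 reports 42.8% and 40.5% by pharmacy records in Arms 1 to 3.
- *That the Western/Eastern term breaks the model.* Its main effect is aliased with county (rank 7 with 8 columns), since "we will adjust for county as a categorical (nominal) variable" already covers it. Software drops the redundant column and no result changes.

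**Conclusion.** The point holds as a worthwhile improvement to a secondary analysis. The planned sex and age modifiers are measured after randomisation in a group whose size depends on arm. They answer an ecological question, cannot give an effect in women or men without extrapolation, and can be biased in either direction. For Arm 1 versus Arm 4 initiation, the SD of the estimate is about 2 to 9 times that from sex-specific counts.

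These sizes rest on the SAP's Table 3 means and CV, and on assumed values for the spread of the share, the sex split, baseline differences and enrolment shift. The smaller the true spread of the share, the worse the planned analysis performs. The calculations were done for sex; age has the same structure but was not simulated. Detectable ratios use two-sided 0.05 and would be larger for both methods at 0.0167. Urban/rural status and region are fixed before randomisation and are not affected.

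**What to change.** Add to section 7.5.1.3 an analysis with two counts per pharmacy: women and men, and separately 25 and under and over 25. Use the section 7.5.1.1 model with the same total-volume offset, county, a main effect of sex (or age group), its interaction with arm, and variance clustered by pharmacy. Report sex- and age-specific rate ratios for each arm against Arm 4, and base any statement about sex or age on these.

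Keep the share-based analysis, described as a pharmacy-level association, and do not present it as an effect within women, men or age groups. The Western/Eastern main effect can be omitted for tidiness, keeping the interaction.

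The cost is SAP wording and a reshaping of data already needed for the share. There are two downsides to state. The addition comes after unblinding, so it must be labelled post hoc and shown beside the planned analysis, as section 7.7 does for imputation. The offset is total transactions, so rate ratios between arms rely on randomisation to balance client mix across 15 pharmacies per arm, and the sex or age main effect is not itself a comparison of rates.

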- Must be willing to use a study-specific module within a digital platform (Maisha Meds) to record pharmacy PrEP/PEP dispensing
- Owner must agree to allow a trained research assistant to come to the pharmacy on select days to collect data from a random subset of participants
- Owner must agree to allow providers to participate in a monitored WhatsApp group, optional surveys, and in-depth interview (IDI)
- Owner must agree to allow providers to routinely engage with a technical assistant

Pharmacists/HTS counselors

Eligibility criteria:

- ≥ 18 years old
- Licensed pharmacist, licensed pharmaceutical technologist, or NASCOP-certified HTS counselor
- Willing to provide PrEP and PEP services, including HIV testing and associated counseling services
- Completed training on PEP/PrEP service delivery at pharmacies, including certification for rapid diagnostic testing
- Able and willing to provide consent
- Complete study training
- Willing to use a study-specific module within a digital platform (Maisha Meds) to document PrEP/PEP services rendered

Clients

Inclusion criteria:

- ≥ 16 years old, including emancipated minors 16-17 years old
- Interested in initiating PrEP or PEP
- Meets all criteria for PrEP or PEP initiation on the Prescribing Checklist, including being at risk for HIV and not having any medical conditions that might contraindicate PrEP/PEP safety
- Able and willing to provide informed consent

Exclusion criteria:

- Unwilling to provide a phone number at which an RA can reach them for completing surveys and communicating important study-related information
- Currently enrolled in any other HIV vaccine or prevention trial
- Having a condition that would preclude provision of informed consent, make study participation unsafe, complicate interpretation of outcome data, or otherwise interfere with achieving study objectives

3. Study Outcomes

Planned primary outcomes are PrEP initiation and PrEP continuation. These outcomes will be defined as follows:

- PrEP initiation: the number of participants at each pharmacy that initiated (i.e., were dispensed) PrEP at the pharmacy or clinic **within 60 days** of initial pharmacy-based screening. *Comparisons between intervention arms and the control will rely on self-*

report from the 60-day client survey, while comparisons between intervention arms will employ pharmacy records.

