- PrEP continuation: the number of participants at each pharmacy that initiated PrEP at the pharmacy or clinic and returned to the pharmacy or clinic and refilled PrEP **within 60 days** of initial pharmacy-based screening. *Comparisons between intervention arms and the control will rely on self-report from the 60-day client survey, while comparisons between intervention arms will employ pharmacy records.*

Secondary outcomes include those related to PrEP initiation, PrEP continuation, PrEP adherence, PEP initiation, PEP-to-PrEP transition, and repeat PEP use.

- PrEP initiation: the number of participants at each pharmacy that initiated (i.e., were dispensed) PrEP at the pharmacy or clinic **within 270 days** of initial pharmacy-based screening
- PrEP continuation:
 - The number of participants at each pharmacy that initiated PrEP at the pharmacy or clinic and returned to the pharmacy or clinic and refilled PrEP **within 270 days** of initial pharmacy-based screening (regardless of any gaps in pill coverage).
 - The number of participants at each pharmacy that initiated PrEP at the pharmacy or clinic and **refilled PrEP at least twice within 270 days** of initial pharmacy-based screening (regardless of any gaps in pill coverage).
 - The number of participants at each pharmacy that initiated PrEP at the pharmacy or clinic and refilled PrEP more than 7 days after their expected refill date (i.e., stopping and restarting, also referred to as “PrEP reinitiation”) **within 270 days** of initial pharmacy-based screening.
- PrEP adherence: The median adherence score (0-100) among participants at each pharmacy who initiated PrEP at the pharmacy or clinic –using the Wilson et al. scale (2020, *AIDS*)—as measured at **60 days** following initial pharmacy screening.
- PEP initiation: the number of participants at each pharmacy that initiated (i.e., were dispensed) PEP ≥ 1 times at the pharmacy or clinic within 3 days, as measured at **60 days** and **270 days** following initial pharmacy screening.
- PEP-to-PrEP transition: the number of participants at each pharmacy that successfully completed PEP (tested negative or self-reported testing negative for HIV between 28 and 45 days after initiating PEP at the pharmacy) **and** initiated PrEP at the pharmacy or clinic as measured at **60 days** and **270 days** following initial pharmacy screening.

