6.2 Data sources

The following data sources will be used to address the objectives (detailed in **Table 5**):

- Pharmacy records: intervention arms only, Arms 1-3 (i.e., not SOC arm, Arm 4)
 - Items on Prescribing Checklist, including PEP/PrEP dispensing data, age, sex, marital/relationship status, behaviors associated with HIV risk, HIV test result
 - Other services/products purchased
- Clinic records: SOC arm only
 - Items on the Clinical Encounter Form akin to those in the study's Prescribing Checklist
- Brief client surveys: all arms
 - Brief demographics
 - Whether the participant initiated PrEP and/or PEP and, if so, where
 - Whether the participant has refilled PrEP and, if so, where
 - Whether the participant is still taking PrEP/PEP as of today
 - If the participant is still taking PrEP/PEP, how many PrEP/PEP pills they swallowed in the past 7 days
 - PrEP adherence
 - Select HIV risk behavior questions

- Extended client survey: all arms
 - Extended demographics
 - Alcohol use
 - Sexual and mental health
 - HIV risk behaviors
 - Fertility
 - Social harm
 - Acceptability of pharmacy model in which they received PrEP/PEP services
 - Quality of care perceptions Fidelity of services received
 - Willingness to pay
- Provider surveys: all arms
 - Provider demographics
 - Acceptability of pharmacy-delivered PrEP/PEP
 - Feasibility of pharmacy-delivered PrEP/PEP
 - Self-efficacy to delivery PrEP/PEP services at pharmacies
 - Organizational Readiness for Change (ORIC)
 - Willingness to charge
- Client in-depth interviews: all arms
 - Model acceptability
 - Model appropriateness
 - Acceptability of modifications
 - Appropriateness of modifications
- Provider in-depth interviews: all arms
 - Acceptability
 - Feasibility
- Technical assistance (TA) reports
 - Adaptations

Data from the Maisha Meds application on PrEP/PEP delivery/dispensing, survey data, audio files from interviews, and interview transcripts will be stored on secure electronic platforms that meet all data security requirements (e.g., REDCap, Dedoose). Table 5 below summarizes the outcomes and data sources.

Table 5. Data sources

PRIMARY/ SECONDARY	OUTCOME	TIMING	DATA SOURCE
Primary	PrEP initiation	By 60 days	Brief client survey Pharmacy records* Clinic records*
	PrEP continuation	By 60 days	
Secondary	PrEP initiation	By 270 days	
	Any PrEP continuation	By 270 days	
	At least 2 PrEP refills	By 270 days	
	Any stopping and restarting PrEP (i.e., PrEP reinitiation)	By 60 and 270 days	

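### Comparisons among Arms 1–3 count only pharmacy-record dispensing, although the outcomes are defined to include clinic dispensing

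*SAP*

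**What the plan says.** Section 3 defines initiation as participants who "initiated (i.e., were dispensed) PrEP at the pharmacy or clinic" within 60 days of screening, and continuation as participants who "initiated PrEP at the pharmacy or clinic and returned to the pharmacy or clinic and refilled PrEP" in the same window. The same two bullets split the data source: the 60-day survey serves comparisons with SOC, "while comparisons between intervention arms will employ pharmacy records".

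Section 7.5.1.3 repeats the split for the comparisons among Arms 1–3. There the outcome "will be computed from the pharmacy records, which is available for all three intervention arms and will be a more complete data source" than the survey, with a cutoff of exactly 60 days. Section 7.5.2 carries the analyses of 7.5.1.3 to the secondary outcomes where they are appropriate.

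Section 6.2 lists "Clinic records: SOC arm only". The brief client survey, given in all arms, asks "Whether the participant initiated PrEP and/or PEP and, if so, where" and "Whether the participant has refilled PrEP and, if so, where".

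Section 7.5.1.3 also plans a descriptive comparison of survey counts with pharmacy-record counts in Arms 1–3. No inferential sensitivity analysis of the Arm 1–3 comparisons brings in clinic events.

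**The concern.** The outcome covers two places of dispensing and the source for these comparisons covers one. A client enrolled at an Arm 1–3 pharmacy who starts or refills at a clinic meets the Section 3 definition but never enters the count. In this cluster-level count model such events drop out of the numerator.

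The reason given for the source addresses a different problem. The records are more complete than the survey about who was dispensed PrEP at the pharmacy, because they do not depend on a survey response. They cannot show clinic dispensing at all.

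Two things are at stake. A reader who sets the SOC comparisons beside the between-model comparisons will take them to be about the same outcome. And if clients of one model use clinics more than clients of another, part of the reported difference in PrEP use is a difference in where PrEP was obtained.

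**Working it through.** **1. The sources side by side**

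| Comparison | Source | Clinic events counted? | Survey non-responders' pharmacy events counted? |
|---|---|---|---|
| Arms 1, 2, 3 vs Arm 4 | 60-day survey | Yes | No, under the prespecified rule in 6.7 |
| Among Arms 1–3 | Pharmacy records | No | Yes |

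The Table 5 footnote names client records alongside pharmacy records for comparisons between intervention arms. Its asterisks sit on pharmacy and clinic records, so this is probably a slip for clinic records. Either way, Section 6.2 lists no clinic source for Arms 1–3.

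**2. Inputs, checked against the plan's own figures**

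Table 3, PrEP initiations per pharmacy: 16.13, 22.18, 26.21, 10.08. Total 15 × 74.60 = 1,119, as stated. Continuations: 8.06, 15.52, 20.97, 6.05. Total 15 × 50.60 = 759, as stated.

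Table 4 power, Arm 1 vs Arm 4, initiation, by the Hayes–Bennett formula with c = 15, CV = 0.25 and two-sided alpha 0.05/3 (z = 2.394):

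- numerator: 14 × (16.13 − 10.08)² = 512.4
- denominator: 26.21 + 0.0625 × (16.13² + 10.08²) = 48.82
- power = Φ(√10.50 − 2.394) = 80.1%, stated as 80%

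These figures are not in dispute. They only confirm the inputs. The SAP gives no planned figure for a comparison among Arms 1–3.

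**3. The bias factor**

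Let s be the share of true pharmacy-or-clinic events that the pharmacy record misses because a needed dispensing was at a clinic. Then

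recorded ratio (a vs b) = true ratio × (1 − s_a)/(1 − s_b).

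Take the client-sustained column against the implementor-sustained column, and treat the Table 3 means as true totals. The true ratios are 16.13/22.18 = 0.727 (initiation) and 8.06/15.52 = 0.519 (continuation). The shares below are assumptions.

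| Clinic share, client- vs implementor-sustained | Factor | Initiation | Continuation |
|---|---|---|---|
| 10% vs 10% | 1.000 | 0.727 | 0.519 |
| 10% vs 5% | 0.947 | 0.689 | 0.492 |
| 20% vs 5% | 0.842 | 0.612 | 0.437 |
| 30% vs 5% | 0.737 | 0.536 | 0.383 |
| 5% vs 10% | 1.056 | 0.768 | 0.548 |

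The factor does not depend on the Table 3 means and is the same for both outcomes at the same shares.

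**4. Whether the planned descriptive check would show it**

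Let r be the survey response. If response is unrelated to the outcome and reports are accurate, survey count / record count = r/(1 − s). With the 75% completion assumed in Section 4.5:

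- s = 0: 0.75
- s = 10%: 0.75/0.90 = 0.83
- s = 25%: 0.75/0.75 = 1.00

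So the two totals could agree exactly while a quarter of events were at clinics. Non-response lowers the survey count and clinic events raise it, and the totals do not separate the two.

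**5. Outcomes that inherit the analysis**

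The 270-day refill outcomes in Section 3 also count clinic dispensing and leave more time to change source. For PrEP reinitiation the error can add events: a client who refills at a clinic on time and later returns to the pharmacy can look, in the pharmacy record, like someone who stopped and restarted.

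**The case against.** The choice of source is open and reasoned. Section 3 names it in the bullets that define the outcomes, and 7.5.1.3 gives two reasons: completeness relative to the survey, and exact dates. Section 7.7 supports the first, since many people who did not answer the survey had started or continued according to pharmacy data. Replacing the records with the survey would bring in non-response that differs by arm. These analyses are also secondary; the stated objective is comparison with SOC, which uses the survey and is untouched. All of this stands. It is why the records should remain the main source here, but it does not make them measure the outcome as defined.

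A reader might go further and infer that the cost of charging clients is overstated, because a client asked to pay has a reason to go elsewhere. The mechanism is plausible, but the SAP does not report clinic use in any intervention arm. Equal shares leave the ratio unbiased, and a larger share in the free arms reverses the direction. Nor does the SAP support saying that continuation is more biased than initiation; that would need different shares for the two outcomes. Any fee contrast also meets a contradiction: the Section 1 overview makes Arm 1 free and Arm 2 the fee arm, while Section 4.5 bases Arm 1 on a pilot that charged a fee and Tables 2 and 3 label it client-sustained.

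**Conclusion.** The mismatch is real and rests on the SAP's text alone. For Arms 1–3 the defined outcome includes clinic dispensing, the source used excludes it, and the planned descriptive check does not isolate it. The between-model and SOC comparisons therefore carry one name for two outcomes.

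Whether the rate ratios are biased, and which way, is unknown. Over the assumed shares in the table the effect runs from none, through about 5% and 16%, to about 26% at 30% vs 5%, and to about 6% in the opposite direction at 5% vs 10%. The worked ratios assume that the client-sustained column is the fee model and that Table 3 gives pharmacy-or-clinic totals. The point concerns secondary analyses and is a matter of labelling plus a missing sensitivity analysis, with no effect on the primary comparisons.

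**What to change.** 1. In Sections 3 and 7.5.1.3, keep the pharmacy-record count as the main result for comparisons among Arms 1–3, but define and report it as PrEP dispensed (or refilled) at the study pharmacy. Apply the same label to the outcomes that inherit this analysis through 7.5.2.
2. Report by arm, among survey responders, the share of initiations and of refills obtained at a clinic.
3. Add a sensitivity analysis that counts an event if the pharmacy record shows it by day 60 or the survey reports it at a clinic. Mark it as not prespecified, because Section 7.7 records that the team has been unblinded.
4. Reconcile Section 1 with Section 4.5 on which arm charges a fee before any fee contrast is read, and correct the source named in the Table 5 footnote.

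The cost is wording, one derived variable and one short table, all from data already collected. The sensitivity analysis has limits that should be stated with it. Clinic events are known only for responders, and Section 7.7 reports that survey completion varied across arms. Survey timing is also looser than the exact 60-day cutoff, since Section 7.5.1.1 does not restrict it in the primary analysis. For these reasons it should stand beside the records-based count and not replace it.
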